#### 9.2.4 Immune related adverse events (irAEs)

irAEs are toxicities from immune checkpoint inhibitors and do not include infusion reactions [38]. For patients in cohorts B and D treated with immunotherapy, all irAEs [38] that occur between the first vaccination and 28 days after the last vaccination will be collected and graded according to CTCAEv5.0. irAEs of grade  $\geq$ 3 are required to be reported to the PI immediately (i.e. no more than 24 hours after learning of the event). The coordinating investigator, the PI or delegated trial personnel will report grade  $\geq$ 3 irAEs through the web portal ToetsingOnline to the accredited METc that approved the protocol, within 15 days of first knowledge of the irAEs that result in death or are life-threatening. All other irAEs will be reported within a period of maximum 15 days.

#### 9.2.5 Suspected unexpected serious adverse reactions (SUSARs)

Adverse reactions are all untoward and unintended responses to an investigational product related to any dose administered.

Unexpected adverse reactions are SUSARs if the following three conditions are met:

- 1. the event must be serious:
  - results in death;
  - is life-threatening (at the time of the event);
  - requires hospitalization or prolongation of existing inpatients' hospitalization;
  - results in persistent or significant disability or incapacity;
  - is a congenital anomaly or birth defect; or

- any other important medical event that did not result in any of the outcomes listed above due to medical or surgical intervention but could have been based upon appropriate judgement by the investigator.

 there must be a certain degree of probability that the event is a harmful and an undesirable reaction to the medicinal product under investigation, regardless of the administered dose; 3. the adverse reaction must be unexpected, that is to say, the nature and severity of the adverse reaction are not in agreement with the product information as recorded in the Summary of Product Characteristics (SPC).

The sponsor will report expedited the following SUSARs through the web portal *ToetsingOnline* to the METC:

- SUSARs that have arisen in the clinical trial that was assessed by the METC;
- SUSARs that have arisen in other clinical trials of the same sponsor and with the same medicinal product, and that could have consequences for the safety of the subjects involved in the clinical trial that was assessed by the METC.

The remaining SUSARs are recorded in an overview list (line-listing) that will be submitted once every half year to the METC. This line-listing provides an overview of all SUSARs from the vaccine, accompanied by a brief report highlighting the main points of concern.

The expedited reporting of SUSARs through the web portal Eudravigilance or ToetsingOnline is sufficient as notification to the competent authority.

The expedited reporting will occur not later than 15 days after the sponsor has first knowledge of the adverse reactions. For fatal or life-threatening cases, the term will be maximal 7 days for a preliminary report with another 8 days for completion of the report.

# 9.3 Annual safety report

In addition to the expedited reporting of SUSARs, the sponsor will submit, once a year throughout the clinical trial, a safety report to the accredited METC and competent authority.

This safety report consists of:

- a list of all suspected (unexpected or expected) serious adverse reactions, along with an aggregated summary table of all reported serious adverse reactions, ordered by organ system, per study;
- a report concerning the safety of the subjects, consisting of a complete safety analysis and an evaluation of the balance between the efficacy and the harmfulness of the medicine under investigation.

#### 9.4 Follow-up of AEs

All solicited AEs, SAEs, AESIs and irAEs will be followed until they have abated, or until a stable situation has been reached. Depending on the event, follow up may require additional tests or medical procedures as indicated, and/or referral to the general physician or a medical specialist.

## **10. STATISTICAL ANALYSIS**

A description of the participant population will be included in a statistical output report, including subgroups of gender, tumor type, treatment, and treatment intent (curative versus non-curative).

Participants who are seropositive to SARS-CoV-2 at baseline and participants who have not received at least one dose of the vaccine will be excluded from the immune response analyses, including the primary analysis. All subjects who received at least one administration of the vaccine will be included in the analyses of AEs, SAEs and AESIs, as well as irAEs for cohorts B and D.

For description of the results of this study, appropriate descriptive statistics will be used, including estimates of variance. For comparisons between patient cohorts and controls, the most robust appropriate statistical tests will be applied, after checking that all assumptions for a specific test are met. We will be fully transparent about the analyses (including scripts for analyses) and will report the testing results of the assumptions. In addition, we will present all individual data points of the primary and secondary study parameters.

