To evaluate vaccination related AEs, patients will be asked to collect solicited local and systemic AEs for 7 days after each vaccination using a questionnaire. Similarly serious AEs (SAEs) will be collected for 7 days after each vaccination. Most patients who receive systemic cancer treatment experience multiple AEs that are cancer treatment related, or disease related. As vaccination related AEs are mainly expected within the first week after vaccination, it is not useful to collect all AEs for a prolonged period. Instead, all newly occurring immune related AEs (irAEs) are collected for the immunotherapy and chemo-immunotherapy cohorts (B and D) up to 28 days after the second and if applicable the third vaccination. irAEs are toxicities from immune checkpoint inhibitors and do not include infusion reactions [38]. Furthermore, adverse events of special interest (AESIs) will be collected for the duration of the study in the patient cohorts.

Information on incidence of SARS-CoV-2 infection, outcome of COVID-19 during 18 months after the second vaccination will be collected using questionnaires. For the study participants who give separate consent, information on positive corona tests during the study will also be collected from the RIVM.

Although this study is not powered to detect differences in protection against COVID-19 between patients and controls, information on incidence of SARS-CoV-2 infection, outcome of COVID-19 will be collected up to 18 months after the second vaccination for descriptive purposes.

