#### 8.1.2 Secondary study parameters/endpoints

- Safety assessment through:
  - Incidence and severity of solicited AEs during 7 days after each vaccination (see Appendix 1)
  - o Incidence and nature of SAEs during 7 days after each vaccination
  - Incidence and nature of newly occurring irAEs [38] grade ≥ 3 in cohort B and D up to 28 days after the last vaccination graded according to the Common Terminology Criteria for Adverse Events version 5.0 (CTCAEv5.0)
  - Incidence, nature and severity of AESIs (see Appendix 2) graded according to CTCAEv5.0
- In depth assessment of immune response through:

- Measurement of SARS-CoV2 specific antibodies before the second vaccination to analyze initial response, and at 6 and 11 and 18 months after the second vaccination to measure longevity
- Measurement of SARS-CoV2 specific antibodies at day 28 after the third vaccination if applicable
- Assessment of SARS-CoV2 specific T cells response at 28 days after the second and third vaccination and at 6, 11 and 18 months after the second vaccination using a high throughput Interferon y ELIspot

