## Table 1: Flow chart/time and events schedule

Procedure	Screening a	Vacc	Vacc	Day	Day	Day	Vacc	Day	Day	Day	Day
	(within 28	1	2	28	90	180	3 m	28	270	330	540 (±
	days)			vacc	(±7)	(± 7)		vacc	(±7)	(± 14)	21)
				2 b				3			
				(± 3)				(± 3)			
Informed consent	х						х				
Inclusion/exclusion											
criteria	x										
Medical history	х										
Concomitant											
medication	x	х	х	х		X	x	х		x	X
Smoking history	х										
ECOG PS b	х										
Height/weight	х						х				
Vital signs c	х	х	х				х				
Blood tests d		х	х	х		х	х	х		х	х
Nasal MLF				х							
collection e		X									
Sollicited adverse				х							
events f	X	X	X				X				
SAEs g		х	х	х			x				
irAEs h	х	х	х	х			х	х			
AESIs i			Will be	e report	ed for t	he entii	re durat	ion of th	ne study		
Vaccine		~	~								
administration j		X	X				X				
COVID-19					~	~					
questionnaire k	X				X	X	X		x	x	x
Survival status						х				x	x

a Screening should be performed within 28 days prior to the first vaccination but can be done on the same day as the first vaccination.

b ECOG performance status: see appendix 3.

c Vital signs: blood pressure, heart rate, temperature.

d See Table 2.

e MLF = mucosal lining fluid, will be collected using a synthetic absorptive matrix [39] f Participants will complete a questionnaire for solicited systemic and local AEs on a daily basis from each vaccination until 7 days after each vaccination, see Appendix 1. g SAEs that occur within 7 days of each vaccination will be reported

h Newly developed irAEs [38] grade  $\geq$  3 need to be reported for cohort B and D up to 28 days after the second vaccination and from the third vaccination to 28 days thereafter.

i AESIs (see Appendix 2) will be reported by the treating physicians up to 18 months after vaccination for cohorts B-D.

j The name of the vaccine, batch number and date and time of administration will be recorded.

k Participants will complete a questionnaire for diagnosis of SARS-CoV-2 infection, severity and outcome of COVID-19.

 Only participants with an inadequate antibody response (≤300 BAU/mL) on day 28 after the second vaccination.

	Vacc1 a	Vacc2 a	Day	Day		Day		Day

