# 9.2.3 Adverse events of special interest (AESIs)

Adverse events of special interest (AESIs) and serious adverse events (SAEs) frequently occur in patients with cancer who receive systemic therapy as a result of the cancer treatment or the underlying disease. Therefore, AESIs will be collected in this study (see Appendix 2). Treating physicians from patients in cohorts B, C and D will report AESIs to the PI. The coordinating investigator, the PI or delegated trial personnel will report the AESIs through the web portal ToetsingOnline to the accredited METC that approved the protocol, within 15 days after first knowledge of the AESIs.

Since the vaccine is a registered agent, and the number of controls in this study is very small compared to the registration trials, AESIs from the control group will not meaningfully add to the existing safety data. Therefore, subjects in the control group will be asked to report potential side effects of vaccination according to the national guidelines for the general population to the Dutch pharmacovigilance center Lareb.

Death of any cause is considered an AESI, because life expectancy of at least 12 months is required for inclusion. We will report deaths and collect information on cause of death. In order to be as complete as possible, informed consent is asked for coupling of data with the Gemeentelijke Basis Administratie (GBA) and Centraal bureaus voor Statistiek (CBS), also from individuals without cancer. However, this is optional and participants who do not consent to coupling of data with CBS and GBA can participate in the study.

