#### **10.2 Secondary study parameters**

- Incidence and severity of solicited AEs during 7 days after each vaccination is a key secondary endpoint (see Appendix 1). Frequencies and absolute numbers of mild, moderate and severe solicited AEs per cohort will be listed for the first, second and third vaccination separately.
- The numbers, nature and severity of SAEs graded according CTCAEv5.0 will be listed per cohort.
- Incidence and nature of newly occurring irAEs grade ≥ 3 in cohorts B and D up to 28 days after the second vaccination is the second safety endpoint. irAEs will be graded according CTCAEv5.0. Frequencies and absolute numbers of all newly occurring irAEs grade ≥ 3 that occur between the first vaccination and 28 days after the second vaccination in cohorts B and D will be listed.
- Incidence, nature and severity of AESIs comprise the third safety endpoint. AESIs will be graded according CTCAEv5.0. Absolute numbers and frequencies of all AESIs will be listed per cohort and subdivided by severity.
- Levels of SARS-CoV-2 S-specific IgG antibodies at 28 days after the second vaccination will be compared between each patient cohort and the non-cancer cohort using ANOVA or Kruskal–Wallis one-way analysis of variance, and Welch ttests or Mann-Whitney U tests, depending on the distribution of the data.
- Levels of SARS-CoV-2 S-specific IgG antibodies before the second vaccination and at 6, 11 and 18months after the second vaccination will be measured to assess early antibody response and longevity. GMCs and 95% CIs will be calculated. The absolute numbers and percentages of responders will be reported for each cohort for each time point. Antibody levels before the second vaccination and at 6, 11 and 18 months will be compared between each patient cohort and the non-cancer cohort using ANOVA or Kruskal–Wallis one-way analysis of variance, and Welch t-tests or Mann-Whitney U tests, depending on the distribution of the data.

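### The AESI analysis covers all vaccinated participants and lists frequencies per cohort, but non-fatal AESIs are collected only in cohorts B to D, so the cohort A entry would be zero or near zero because nobody looked

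*Combined protocol and SAP*

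**What the plan says.** **Analysis text.** Section 10 defines the safety set: "All subjects who received at least one administration of the vaccine will be included in the analyses of AEs, SAEs and AESIs". The same sentence goes on to limit irAEs to cohorts B and D, but sets no such limit for AESIs. Section 10.2 calls AESIs the third safety endpoint and says: "Absolute numbers and frequencies of all AESIs will be listed per cohort and subdivided by severity". The endpoint line in section 8.1.2 reads "Incidence, nature and severity of AESIs (see Appendix 2) graded according to CTCAEv5.0", again with no cohort limit, although the irAE line just above it has one. Section 10 also promises, for the results in general, that "appropriate descriptive statistics will be used, including estimates of variance".

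**Collection text.** Section 3 says that "adverse events of special interest (AESIs) will be collected for the duration of the study in the patient cohorts". Footnote i of Table 1 says that AESIs "will be reported by the treating physicians up to 18 months after vaccination for cohorts B-D". Section 9.2.3 names the treating physicians of cohorts B, C and D as the reporters and gives a reason for leaving out controls: "AESIs from the control group will not meaningfully add to the existing safety data". Controls are asked instead to report side effects to the national pharmacovigilance centre.

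**Deaths.** Section 9.2.3 and Appendix 2 count death from any cause as an AESI. The survival-status row of Table 1 (days 180, 330 and 540) has no cohort limit, and optional consent to registry linkage is asked "also from individuals without cancer".

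**The concern.** The collection rule and the analysis rule do not match. Leaving controls out of AESI collection is a deliberate and reasoned choice. The analysis text does not carry that choice through, and instead puts controls in the denominator and gives them a place in the per-cohort listing.

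A frequency of zero is informative only if the events were looked for. Here, a cohort A entry at or near zero for non-fatal AESIs would stand beside entries for cohorts B to D that were collected for up to 18 months. A reader could take the gap for an observed difference between patients and controls. Section 13 raises this very question, since it says that patients on cancer treatment might have a higher risk of vaccination-related adverse events.

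**Working it through.** The documents give no AESI count or rate, so there is no figure of the plan's own to reproduce. The check sets the passages side by side and then does simple arithmetic on the planned cohort sizes.

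**1. What is captured in cohort A**

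| Event type | Captured in cohort A? | Source |
|---|---|---|
| Non-fatal AESI, reported as an AESI | No | Section 3; Table 1 footnote i; section 9.2.3 |
| Serious event within 7 days of a dose | Yes, as an SAE | Sections 8.1.2 and 9.2.2 |
| Death | Yes | Table 1 survival status; optional registry linkage, section 9.2.3 |
| Side effects reported to the pharmacovigilance centre | No return to the study is described | Section 9.2.3 |

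The documents do describe external data coming into the study for deaths (section 9.2.3) and for positive SARS-CoV-2 tests (section 3). They describe nothing similar for side-effect reports.

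**2. What is analysed in cohort A.** Section 10 includes everyone with at least one dose, and section 10.2 lists AESIs per cohort. Cohort A therefore appears with its full denominator.

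**3. Planned numbers (section 4.4):** A 246, B 135, C 246, D 246.

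- AESI set as written: 246 + 135 + 246 + 246 = 873.
- Cohorts in which non-fatal AESIs are collected: 135 + 246 + 246 = 627, and 627/873 = 71.8%.
- In the set, but without non-fatal AESI collection: 246/873 = 28.2%.

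**4. How the cohort A entry would look.** If the general promise of variance estimates were applied to this listing, the exact (Clopper-Pearson) 95% intervals would be:

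- 0/246: upper limit = 1 − 0.025^(1/246) = 1.49%, so 0 to 1.49%.
- 1/246 = 0.41%: interval 0.01% to 2.24%.
- Sensitivity to the denominator: section 1.6 reports 240 cohort A participants evaluable for the primary endpoint (the size of the safety set is not given). For 0/240 the upper limit is 1 − 0.025^(1/240) = 1.53%.

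These intervals show only how precise the entry would appear. They do not measure the bias, and they leave deaths out.

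**5. What cannot be computed.** The number of AESIs missed in cohort A would need an AESI rate, which the documents do not give. Spreading a rate evenly over 18 months is not supported either, because section 3 expects vaccination-related events mainly in the first week.

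**The case against.** The strongest reply is that this is loose drafting. The limit to cohorts B to D is stated three times, once with its reason, and an analyst who knows the protocol would not print an uncollected item as zero. A listing per cohort can be read as one for each cohort in which AESIs are collected. The adverse-event objective in section 2 is itself worded for patients with cancer only, and the open category in Appendix 2 depends on the judgement of a treating physician. That reading is plausible as to intent, but the text does not secure it. The section 10 sentence sets a cohort limit for irAEs and none for AESIs, and sections 8.1.2 and 10.2 follow the same pattern. The patient-only objective supports narrowing the set.

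Second, an all-vaccinated set is correct for deaths, which count as AESIs. This stands. The problem is confined to non-fatal AESIs, and deaths need that wider set.

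Third, section 8.6 names AESIs among the monitored events, with a day 7 window for cohorts A and C, which suggests some AESI monitoring in cohort A. But that section concerns subjects withdrawn from treatment and refers back to the protocol, and its window for cohort C conflicts with the 18 months in Table 1. It is a further inconsistency to reconcile. It does not outweigh the three explicit statements.

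Fourth, section 10.2 specifies numbers and frequencies without intervals, and no pooled AESI rate. This also stands: the intervals above depend on applying a general sentence of section 10 to this listing, and the 71.8% to 28.2% split describes the set without distorting any planned estimate.

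**Conclusion.** The point holds. As written, the plan would report a non-fatal AESI frequency for 246 planned controls in whom those events are not collected. The entry would be at or near zero whatever the true incidence.

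Its importance is modest. The rates in cohorts B to D and the primary analysis are unaffected, no test of AESIs between cohorts is specified, and the damage is limited to a descriptive safety listing that invites a false comparison. The size of the under-count is unknown.

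The conclusion rests on two readings: that sections 3 and 9.2.3 and Table 1 take precedence over section 8.6, and that reports to the pharmacovigilance centre do not return to the study, since no such return is described.

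**What to change.** - **Sections 10 and 10.2:** define the non-fatal AESI analysis set and listing as vaccinated participants in cohorts B, C and D (627 planned). Show cohort A as *not collected*, not as 0.
- **Section 8.1.2:** add the same cohort limit to the AESI line for non-fatal events.
- **Deaths:** report them for all four cohorts on a separate line using the all-vaccinated set. State how many participants have unknown survival status, and label registry-linkage results as coming from those who consented to linkage.
- **Section 8.6:** reconcile its AESI windows and cohorts with sections 3 and 9.2.3 and Table 1.

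The cost is wording in sections 8.1.2, 8.6, 10 and 10.2, with no new data collection. The listing will show no control rate for non-fatal AESIs, but none was being measured, so nothing valid is lost.

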#### 10.1 Primary study parameter

The primary study parameter is the antibody based immune response to vaccination against COVID-19 on day 28 after the second vaccination in cancer patients as compared to individuals without cancer. SARS-CoV-2 S-specific serum IgG antibody concentrations will be measured at the RIVM using a validated fluorescent bead-based multiplex-immunoassay [40]. Geometric mean concentrations (GMCs) and 95% confidence intervals (CIs) will be calculated for the SARS-CoV-2 S-protein-specific IgG antibodies at baseline and day 28 after vaccination for each cohort. Participants will be classified as responders or non-responders. The definition of response is seroconversion defined as presence of SARS-CoV-2 spike S1-specific IgG antibodies with a threshold for seropositivity based on Receiver Operator Curve (ROC) analysis and set at 1.04 AU/mL [41]; in individuals without measurable anti-S antibodies at baseline. Concentrations have been interpolated from a reference consisting of pooled sera using a 5-parameter logistic

fit that was calibrated against the NIBSC/WHO COVID-19 reference serum 20/136 and expressed as international binding antibody units per ml (BAU/mL). The value of 1.04 AU/mL corresponds to 10 BAU/mL. Participants who are seropositive at baseline will not be included in the analysis of the primary endpoint. The percentage of responders and corresponding 95% CI for each cohort will be calculated. The percentage of responders of each patient cohort will be compared with the percentage responders in the group without cancer, using a modified standard fixed-delta test [42].

#### **10.2 Secondary study parameters**

- Incidence and severity of solicited AEs during 7 days after each vaccination is a key secondary endpoint (see Appendix 1). Frequencies and absolute numbers of mild, moderate and severe solicited AEs per cohort will be listed for the first, second and third vaccination separately.
- The numbers, nature and severity of SAEs graded according CTCAEv5.0 will be listed per cohort.
- Incidence and nature of newly occurring irAEs grade ≥ 3 in cohorts B and D up to 28 days after the second vaccination is the second safety endpoint. irAEs will be graded according CTCAEv5.0. Frequencies and absolute numbers of all newly occurring irAEs grade ≥ 3 that occur between the first vaccination and 28 days after the second vaccination in cohorts B and D will be listed.
- Incidence, nature and severity of AESIs comprise the third safety endpoint. AESIs will be graded according CTCAEv5.0. Absolute numbers and frequencies of all AESIs will be listed per cohort and subdivided by severity.
- Levels of SARS-CoV-2 S-specific IgG antibodies at 28 days after the second vaccination will be compared between each patient cohort and the non-cancer cohort using ANOVA or Kruskal–Wallis one-way analysis of variance, and Welch ttests or Mann-Whitney U tests, depending on the distribution of the data.
- Levels of SARS-CoV-2 S-specific IgG antibodies before the second vaccination and at 6, 11 and 18months after the second vaccination will be measured to assess early antibody response and longevity. GMCs and 95% CIs will be calculated. The absolute numbers and percentages of responders will be reported for each cohort for each time point. Antibody levels before the second vaccination and at 6, 11 and 18 months will be compared between each patient cohort and the non-cancer cohort using ANOVA or Kruskal–Wallis one-way analysis of variance, and Welch t-tests or Mann-Whitney U tests, depending on the distribution of the data.

SARS-CoV-2 specific T cell response will be measured at baseline, and at 28 days after the second and third vaccination, and 6, 11 and 18 months after the second vaccination and expressed as the number of IFN-γ producing SARS-CoV2 specific T cells/million PBMC. To assess the contribution of CD8+ T cells in this response, we will assess the number of IFN-γ producing T cells after blocking with an MHC class I antibody. This will be expressed as the number of IFN-γ producing CD4+ T cells/ million PBMCs. Subtraction of the number of responding CD4+ T cells from the total number of responding T cells will lead to the number of IFN-γ producing CD8+ T cells/ million PBMCs. Results will be compared between each patient cohort and the cohort of individuals without cancer using ANOVA or Kruskal–Wallis one-way analysis of variance, and Welch t-tests or Mann-Whitney U tests, depending on the distribution of the data.

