influenza vaccination [34]. However, it is striking how little information is available on safety and efficacy of vaccination in cancer patients. As compared to the healthy population, patients with cancer treated with immunotherapy and/or chemotherapy may be more prone to adverse events of vaccination. Immunotherapy could potentially result in an augmented immune response to vaccination resulting in fever, chills, and other immune-related adverse events. Chemotherapy is known for significant fatigue, which impacts performance status and increases vulnerability. As a result, immunotherapy and chemotherapy may have a significant impact on the effectiveness but also on the safety of COVID-19 vaccination. In several countries including Belgium and France, immunocompromised patients are now offered a third vaccination. An advice from the Dutch Health Council about additional vaccination of immunocompromised patients in the Netherlands is expected soon. To protect patients with cancer from COVID-19, clinical trials are urgently needed to evaluate whether they develop an effective, safe, and durable immune response during immunotherapy and/or chemotherapy.

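### The irAE endpoint is limited to undefined new-onset events of grade 3 or higher, so worsening of an existing irAE may go uncounted, and the collection rules conflict

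*Combined protocol and SAP*

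**What the plan says.** Section 8.1.2 sets the endpoint as incidence and nature of "newly occurring irAEs [38] grade ≥ 3 in cohort B and D up to 28 days after the last vaccination". Section 10.2 repeats it as the second safety endpoint and says what will be tabulated: "Frequencies and absolute numbers of all newly occurring irAEs grade ≥ 3", counted from the first dose until 28 days after the second. Footnote h of Table 1, which sites use as their schedule, asks for reporting of newly developed irAEs of grade 3 or higher in the same two cohorts. None of these places defines *newly occurring* or *newly developed*, or says how to class a known irAE that recurs or worsens after a dose.

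The collection rules are wider. Section 3 states that "all newly occurring immune related AEs (irAEs) are collected for the immunotherapy and chemo-immunotherapy cohorts (B and D"), with no grade limit. Section 9.2.4 goes further: "all irAEs [38] that occur between the first vaccination and 28 days after the last vaccination will be collected and graded according to CTCAEv5.0", with no limit to new events and no grade limit. It then requires grade 3 or higher irAEs to go to the PI within 24 hours.

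**The concern.** Section 1.4 gives the reason for watching these cohorts: "Immunotherapy could potentially result in an augmented immune response to vaccination resulting in fever, chills, and other immune-related adverse events". It does not mention flares of existing irAEs. Still, worsening of an irAE that a patient already has is a natural thing to look for when a vaccine is given during checkpoint inhibitor treatment. If the endpoint counts only first onsets, a rise from low grade to grade 3 or 4 after a dose could be missing from the one table meant to describe irAE safety. If sites also follow different collection rules, that table will mix different recording practices and its frequencies will be hard to interpret.

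**Working it through.** No power or sample-size figure depends on this endpoint, and the plan states no target for it. The check is a comparison of the text.

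**1. The five statements side by side**

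| Place | New events only? | Grade limit | End of window |
|---|---|---|---|
| Section 3 (collection) | yes | none | 28 days after dose 2 and, if given, dose 3 |
| Section 8.1.2 (endpoint) | yes | 3 or higher | 28 days after last dose |
| Table 1, footnote h (reporting) | yes | 3 or higher | 28 days after dose 2; dose 3 to 28 days after |
| Section 9.2.4 (collection) | no | none to collect; 3 or higher for immediate reporting | 28 days after last dose |
| Section 10.2 (listing) | yes | 3 or higher | 28 days after dose 2 |

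They disagree on newness and on grade. The windows are also worded differently, though section 10.3 refers third-dose safety back to section 10.2. The point here is which events count, not the window.

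**2. Can affected patients enrol?** Section 4.3 lists no exclusion for a current or past irAE. It does exclude systemic corticosteroids above 10 mg daily prednisone equivalent (adrenal replacement aside) and other immunosuppressants within 14 days of vaccination. That removes patients whose irAE needs such treatment. Patients with a milder or controlled irAE remain eligible.

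**3. Two test cases**

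- *Grade 1 colitis at screening, grade 3 on day 14 after dose 2.* Sections 8.1.2 and 10.2 and footnote h: not counted if new means first onset; counted if new means newly at grade 3. Section 3: not a new irAE, so not named. Section 9.2.4: most naturally collected and reported at once, since it has no newness limit.
- *First onset of a grade 2 irAE.* Sections 3 and 9.2.4: collected. Footnote h: not mentioned.

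**4. Do other routes catch the first case?** SAEs are collected for 7 days after each dose (sections 8.1.2 and 9.2.2), so day 14 falls outside. As an illustration, assume doses 28 days apart, the phase III schedule described in section 1.3. The two-dose irAE window is then 28 + 28 = 56 days, the SAE windows cover 7 + 7 = 14 days, and 14 / 56 = 25%. Appendix 2 does not name colitis, hepatitis or pneumonitis as an AESI. Unless such a flare also meets a listed item, it enters only through the category left to the treating physician. Both routes are partial, and neither places the event in the irAE listing.

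**5. Is a baseline grade available?** Table 1 marks irAEs at screening, which suggests that baseline status is meant to be noted. The mark carries footnote h, and no section says that the grade of an existing irAE is recorded.

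**The case against.** - **The endpoint does not state an exclusion.** A rise from grade 1 or 2 to grade 3 can be read as a newly occurring grade 3 event. This stands: a reader might infer that flares are excluded outright, but the documents support only that this is the ordinary reading of an undefined term. The two readings are themselves the problem.
- **The events are not necessarily lost.** Section 9.2.4 collects and grades all irAEs in these cohorts, and some flares enter as SAEs or AESIs. This also stands, and it limits the point to the irAE listing and to consistent recording.
- **The grade conflict is partly collecting versus reporting.** Section 9.2.4 separates the two. Footnote h speaks of what must be reported and does not tell sites to record nothing else, so it would be too strong to say that a site following Table 1 records no lower-grade events. But footnote h does not say that lower grades are still collected. Sections 3 and 9.2.4 also still differ on newness.
- **A limit to new events is a reasonable filter.** Background toxicity is high in these patients, as section 3 notes, and there is no comparator for this endpoint. A flare could also reflect continuing checkpoint inhibitor treatment. That is a good argument for listing worsened events separately, and a weak one for leaving them out.

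**Conclusion.** The point holds as a definition gap plus inconsistent collection rules. On the ordinary reading, the irAE listing omits worsening of an existing irAE to grade 3 or higher; on the other reading it includes it; and nothing tells sites which applies. The expected result is some under-counting in the listing and recording that differs between sites.

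Its size cannot be estimated from the documents. A reader might take the 131 + 143 = 274 evaluable patients of cohorts B and D in section 1.6 and multiply by a guessed share with an irAE at screening. The documents do not support that. The 274 is the population evaluable for the primary endpoint, whereas section 10 bases irAE analyses on everyone given at least one dose. No share with an irAE at screening and no flare rate is given.

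A reader might also infer that the endpoint is biased towards showing no signal exactly where the protocol expects one. Section 1.4 says only that immunotherapy might augment the response to vaccination, not that vaccination is expected to worsen irAEs. The endpoint is also descriptive, with no test attached. Sample size and the primary analysis are unaffected. This is a cheap improvement.

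**What to change.** 1. In sections 8.1.2 and 10.2 and footnote h, define the endpoint as irAEs of grade 3 or higher that are new, or that have increased in grade from the status at screening. List new and worsened events separately, so that the count of new events alone stays visible.
2. Use one collection rule in sections 3 and 9.2.4 and Table 1: record all grades, with immediate reporting for grade 3 or higher as section 9.2.4 already states.
3. State that irAE status and grade are recorded at screening, where Table 1 already has a mark.
4. Section 1.6 shows that the two-dose results are already in. For doses already given, apply the definition to the section 9.2.4 data and to medical records where available. If sites recorded only new events of grade 3 or higher, report that as a limitation. The final report falls due within a year of study end (section 12.5), so the tabulation can still be set right.

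The cost is rewording in a few places, one more row in the safety table, and slightly more irAE recording in cohorts B and D, which section 9.2.4 already requires. Baseline grades may be incomplete for the first two doses, and new wording cannot recover grades that were never recorded.
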